### **13.3 Sample Size (8/20/10)**

This trial will accrue 75 patients fully evaluable for the DLT toxicity analysis.

Monte Carlo simulation was used to assess the operating characteristics of this design. Complete trials (2,250 for each trial scenario considered) were simulated using 3 different assumptions about the true probabilities of dose-limiting toxicity at each dose: 1) as assumed; 2) somewhat more toxic than assumed; 3) more toxic than assumed with significant increase in toxicity between doses 6 and 7. Among the operating characteristics considered in the sample size were the expected number of dose-limiting toxicities, the probability of selecting the correct dose (that associated with a 20% probability of DLT) as the target dose at the end of the trial, the time required to complete the trial, and the number of patients treated at or near the target dose. Sample sizes from 30 to 120 were evaluated, as were different rates of patient accrual. A sample size of 75 patients was determined to have acceptable probability of correctly selecting a dose with acceptable toxicity and enough patients treated about the target dose for characterization of the efficacy endpoints, while being feasible for completion of accrual within 4 years.

A patient is fully evaluable for toxicity analysis if:

1. The patient fails to complete treatment due to a DLT.  
OR
2. The patient receives all five RT fractions of the protocol treatment.  
AND
  - A. Experiences a DLT within 1 year from the initiation of treatment  
OR
  - B. Is observed per protocol for 1 year after the initiation of treatment and does not experience a DLT

Patients who complete protocol treatment but have progressive disease and no DLT within 1 year are still considered at risk for a DLT even if they receive chemotherapy. It is not likely that the addition of chemotherapy will greatly affect the occurrence of a SBRT-related DLT, and we did not want to exclude patients at risk of DLT.

A patient who does not complete protocol treatment because of non-protocol, treatment-related toxicity; non-protocol, treatment-related death; or refusal to complete protocol treatment will not be evaluable.

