Patients who complete protocol treatment but cannot be observed for a DLT for 1 year (e.g., due to death from other than toxicity or patient refusal) will not count towards the accrual goal, but their data will be used to allocate doses to subsequent patients and in the final analyses for toxicity, primary tumor control and survival, they will be weighted, as appropriate, by the proportion of the observation period they have completed. Note: Patients, who have experienced a DLT, are fully weighted.

It is anticipated that average accrual will be 2 patients per month. Based upon RTOG 0236 (another RTOG trial utilizing SBRT), it is projected that 80% of patient entries will be evaluable for DLT analysis. So to accrue 75 evaluable patients, a total of **94 patients** will have to be entered, and this will take 4 years to complete.

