### **13.5 Analysis Plan**

#### **13.5.1 Analysis of the Primary Endpoints (8/20/10)**

All patients evaluable per Section 13.3 will be used in the DLT analysis (the primary endpoint of the phase I portion), which will be performed after they have been potentially followed for the 1 year observation period. The patients treated at the MTD of SBRT will be used to estimate the 2-year primary tumor control rate (the primary endpoint of the phase II portion), which will be performed after they have been potentially followed for 2 years. Patients not evaluable will be reported separately. For each such patient, the reason for exclusion, protocol treatment received, and toxicities reported during the first year will be listed.

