**13.5.1.2** 2-year Primary Tumor Control Rate at MTD (8/20/10)

Primary tumor control is the absence of local progression (defined as local enlargement confirmed by PET or biopsy which occurs within 2 years from the start of treatment). Marginal failures, which are mentioned in Section 11.3.3, will be considered events for local progression. Distant metastases from the index lung cancer or a second primary tumor are not considered local progression. Patients who die with lung cancer but no documented local progression will be considered non-failures and will be censored on the day of their death. Patients who die without progressive lung disease and have no documented local progression will be considered non-failures and will be censored on the day of their death. Cumulative incidence method will be used to estimate the 2-year primary tumor control rate at the MTD of SBRT. Using this confidence interval, the null hypothesis that the probability of 2-year primary tumor control at the selected target dose (MTD) is 0.7 or less will be tested. Ninety percent confidence interval for the probability of response will be constructed by bootstrapping.

**13.5.2** Analysis of Secondary Survival Endpoints

**13.5.2.1** Progression-Free Survival and Overall Survival (8/20/10)

The same patients used for DLT analysis will be used in these analyses, which will be performed after they have been potentially followed for 2 years. The failure event for progression-free survival (PFS) is defined as the first occurrence of local and/or regional disease progression, distant metastases, second primary tumor, or death due to any cause. Time to PFS is measured from the date of randomization to the date of the failure event for PFS. Overall survival (OS) time is measured from the date of randomization to the date of death due to any cause.

Kaplan-Meier estimation will be used to calculate OS and PFS rate at each radiation dose level. Cox proportional hazards regression will be used to characterize PFS and OS as a function of dose. As in the analysis of 2-year primary tumor control, possible confounding baseline demographic or clinical variables will be included in the regression model if there is evidence of significant imbalance between doses.

**13.5.2.2** Local Progression, Regional Failure, and Distant Metastases

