The same patients for DLT analysis will be used in these analyses, which will be performed after they have been potentially followed for 2 years.

The failure event for local progression (LP) is defined as local enlargement confirmed by PET or biopsy or a marginal failure per Section 11.3.3. The failure event for regional failure (RF) is defined as the first appearance of regional nodal disease. The failure event for distant metastases (DM) is defined as the first appearance of a distant metastases. The time to failure for these secondary endpoints (LP, RF, and DM) will be measured from the date of randomization to the date of the failure event.

The cumulative incidence method will be used to estimate the rates of each endpoint. The treatment effect on these failures may impact the observable measures of outcomes, and other competing risks may dilute the sensitivity. Therefore, Fine and Gray's proportional hazards regression will be used to characterize LP, RF, and DM as a function of dose. Possible confounding baseline demographic or clinical variables will be included in the regression model if there is evidence of significant imbalance between doses.

**13.5.3** Analysis of Secondary Toxicity Endpoints

**13.5.3.1** Any Grade 3 or Worse Toxicity Other Than a DLT Occurring Within the First Year (7/27/10)

This endpoint is defined as any grade 3 or worse toxicity (per CTCAE, v. 4) other than a DLT **occurring within the first year** that is possibly, probably, or definitely related to treatment and occurs within 1 year from the start of SBRT. The distribution of this toxicity will be tabulated by grade and category for each assigned dose level and actual dose received. If the number of applicable toxicities is adequate for analysis, logistic regression will be used to model the distribution of acute adverse events with and without adjustment for demographic or clinical variables.

**13.5.3.2** Late Grade 3 or Worse Toxicity (7/27/10)

This endpoint is defined as any grade 3 or worse toxicity (per CTCAE, v. 4) that is possibly, probably or definitely related to treatment and **occurs after 1 year** from start of SBRT. The distribution of this toxicity will be tabulated by grade and category for each assigned dose

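### Sections 13.3 and 13.5 conflict on who enters the OS, PFS and failure analyses; either rule overstates overall survival, because year-1 deaths without a DLT are dropped or down-weighted

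*Protocol*

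**What the plan says.** Two sets of sentences in the protocol govern who is in the secondary efficacy analyses.

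- **The evaluable-set rule.** Section 13.5.2.1 (OS and PFS): "The same patients used for DLT analysis will be used in these analyses". Section 13.5.2.2 (local progression, regional failure, distant metastases): "The same patients for DLT analysis will be used in these analyses". Section 13.5.1 identifies that set: "All patients evaluable per Section 13.3 will be used in the DLT analysis", with non-evaluable patients reported separately. Under 13.3, a patient who finishes treatment without a DLT is fully evaluable only if the patient "Is observed per protocol for 1 year after the initiation of treatment and does not experience a DLT".
- **The weighting rule.** Section 13.3 then turns to patients who complete treatment but cannot be observed for a year, and gives non-toxic death and refusal as examples. They do not count towards the 75, "but their data will be used to allocate doses to subsequent patients and in the final analyses for toxicity, primary tumor control and survival", where "they will be weighted, as appropriate, by the proportion of the observation period they have completed".

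Section 13.5.2.1 starts the OS clock at the date of randomization. This is a dose-finding trial without randomised arms, so I read that as study entry. OS and PFS use Kaplan-Meier and Cox methods; the failure endpoints use cumulative incidence and Fine-Gray regression.

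**The concern.** A patient who finishes SBRT and dies at month 4 of cancer or comorbidity, without a DLT, is outside the set under the first rule and counts as 4/12 of a patient under the second. In both cases the death that OS is meant to count decides how far the patient counts. A patient who lives through the year always counts in full.

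The fractional weight belongs to the TITE-CRM likelihood (13.4.1), where a DLT-free patient at 4 months carries only part of the information about a 12-month DLT. It has no such role in a survival analysis. A death at 4 months is a complete OS observation, and incomplete follow-up is already handled by censoring.

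Section 3.1.2.2 restricts entry to patients with severe underlying health problems, so non-toxic deaths in the first year are foreseeable. At stake is the credibility of the survival rates reported for this regimen (objective 2.2.3).

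**Working it through.** **1. The plan's own figure.** 75 evaluable patients at an 80% evaluable share: 75 / 0.80 = 93.75, rounded up to 94. At 2 per month this takes 47 months. The stated 94 and 4 years reproduce. Up to 94 − 75 = 19 patients are projected as non-evaluable. The protocol does not say how many of these would be early deaths.

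**2. Simple bound on 1-year OS.** Let k of the 19 be DLT-free deaths in year 1. Assume that no evaluable patient dies in year 1 and that the other non-evaluable patients are set aside. True 1-year OS is 75/(75 + k). The evaluable-only set gives 75/75. With an assumed average weight of 0.5, the weighted set gives 75/(75 + 0.5k).

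| k | True | Evaluable only | Weighted |
|---|---|---|---|
| 5 | 93.8% | 100% | 96.8% |
| 10 | 88.2% | 100% | 93.8% |
| 15 | 83.3% | 100% | 90.9% |
| 19 | 79.8% | 100% | 88.8% |

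**3. 2-year OS, allowing deaths after a DLT to count.** Assumptions:

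- exponential deaths with 1-year survival S and rate λ = −ln S;
- DLT probability p = 0.20 (the target rate), flat over the year as 13.2 assumes, and independent of death;
- no loss to follow-up.

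Define M1 = (1 − S)/λ − S and M2 = 2·M1/λ − S. These are the integrals of u and u² against the density of death over year 1. A patient who dies at u years has had a DLT first with probability p·u. Then:

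- evaluable share E = S + p·M1;
- total weight under the 13.3 rule W = E + M1 − p·M2;
- 2-year OS is S² in all treated patients, S²/E in the evaluable set and S²/W in the weighted set.

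For S = 0.80: λ = 0.2231, M1 = 0.0963, M2 = 0.0630, E = 0.8193, W = 0.9029. The 2-year OS is 0.640 in all treated, 0.640/0.8193 = 0.781 evaluable-only, and 0.640/0.9029 = 0.709 weighted.

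| Assumed 1-year OS | All treated, 2-year | Evaluable only | Weighted | Overstatement (points) |
|---|---|---|---|---|
| 95% | 90.2% | 94.5% | 92.4% | 4.3 / 2.2 |
| 90% | 81.0% | 89.0% | 85.0% | 8.0 / 4.0 |
| 85% | 72.2% | 83.6% | 77.9% | 11.3 / 5.6 |
| 80% | 64.0% | 78.1% | 70.9% | 14.1 / 6.9 |

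A simulation of 2 million patients per case gives the same values to within about 0.1 point. One-year OS in the evaluable set (S/E) runs from 99.5% down to 97.6%, against a true 95% to 80%. It is not exactly 100%, because patients who die after a DLT remain in the set.

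**4. The other endpoints.** Each dropped early death is also a PFS event in year 1, so PFS should move the same way; this was not computed. For local, regional and distant failure, dropping early deaths removes competing deaths, which raises cumulative incidence. It also removes failures among those who died, which lowers it. The net sign is open.

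**The case against.** **The protocol does keep these patients.** Section 13.3 says that their data enter the final analyses. The table outline in 13.5.1.1 lists patients still at risk for a DLT under the evaluable heading, so that word need not mean a completed year. This stands to the extent that a flat statement that early deaths are excluded goes too far. It does not clear the plan. Section 13.3 itself uses the narrow sense when it projects an 80% evaluable share, 13.5.1 sets non-evaluable patients apart, and the sentence that rescues them gives an early death a weight below 1.

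**The weighting applies only "as appropriate", and an analysis plan could settle it.** That qualifier does not make a DLT-window weight valid for a death. The sentence names survival, so this is a stated rule and not detail left for later.

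**The bias may be smaller than the top of the range.** Appendix VII shows 55 patients at risk at the start in RTOG 0236 and 46 at 9 months, with 4 DLTs. So 55 − 46 − 4 = 5 left DLT-free for any reason, which is 9.1% by 9 months, or 1 − (50/55)^(12/9) = 11.9% over a year at a constant rate. That caps DLT-free death in that trial, which treated peripheral tumors. At 1-year OS of 88%, the formulas above give about 9 points under exclusion and 5 under weighting. This is a fair middle case, inside the stated range.

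**No decision depends on it.** The MTD is unaffected, the phase II primary endpoint has its own set (patients treated at the MTD), and no test uses OS or PFS. Reports also list all entered cases with exclusions. All true: the harm is to reported secondary estimates, and listing exclusions shows a reader the problem without correcting the estimates.

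**Conclusion.** The point holds as an unreconciled conflict between 13.3 and 13.5 over the survival population, with OS biased upward under either rule and PFS expected to follow. With 1-year OS of 95% to 80%, exponential deaths and a DLT probability of 0.20, 2-year OS is overstated by about 4 to 14 points if early deaths are dropped, and about 2 to 7 if they are weighted. The size rests on those assumed survival rates, since the protocol gives none; the direction for OS does not.

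Three stronger readings are tempting and are not supported:

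- *Every Kaplan-Meier, Cox, cumulative-incidence and Fine-Gray result favours SBRT.* There is no comparator arm, the regressions model outcome against dose, and the direction for local, regional and distant failure is not fixed.
- *The whole projected 20% non-evaluable share is early death.* Section 13.3 also counts incomplete treatment and refusal.
- *Early deaths are simply excluded.* Section 13.3 says otherwise for those who completed treatment.

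**What to change.** - **Sections 13.5.2.1 and 13.5.2.2:** replace the reference to the DLT patients with all eligible patients who start protocol SBRT, each at full weight. Censor OS and PFS at last follow-up. For local progression, regional failure and distant metastases, treat death without the event as a competing risk, as the cumulative incidence method already named there requires.
- **Section 13.3:** limit the evaluability rule and the time-on-study weights to the DLT model. State that patients not observed for a full year are included at full weight in the tumor control and survival analyses. Simply deleting the present sentence would not do, because it is the only one in 13.3 that keeps these patients in.
- **Section 13.5.1:** make clear that separate reporting of non-evaluable patients concerns the DLT analysis only.

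The cost is a wording change. Reported survival will be less favourable than under the present rules. The MTD, dose assignment and the sample size of 94 do not change.

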### **2.2 Secondary Objectives (8/20/10)**

**2.2.1** To estimate rates of ≥ grade 3 CTCAE, v. 4 adverse events other than a dose-limiting toxicity (DLT) which is possibly, probably, or definitely related to treatment and which occurs within 1 year from the start of SBRT;

**2.2.2** To estimate rates of late (> 1 year from start of SBRT) adverse events;

**2.2.3** To estimate the primary tumor control and progression-free and overall survival rates for patients treated with this regimen;

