### **6.9** (2/16/10) Radiation Therapy Adverse Events

The rationale for this phase I/II study is to determine the safe SBRT dose schedule for centrally-located NSCLC, i.e., within the proximal bronchial tree. There is concern about RT effects on organs at risk, most notably central airway, esophagus and heart/pericardium, as these organs

will be in immediate proximity to the centrally-located tumors. **See Section 13.1.1 for definitions of dose-limiting toxicities for this study.**

**6.9.1** Cardiac and Pericardial Injury

Although cardiac and pericardial injury is uncommon in the conventionally fractionated course of RT, with large doses per fraction of SBRT a number of possible side-effects can be seen.

**6.9.2** Gastrointestinal/Esophageal Injury

The radiation effects on the esophagus can be acute: esophagitis (i.e., dysphagia, causing pain on swallowing, typically relatively soon after RT course is completed, and typically resolves on its own within days to a week or longer), or chronic, typically manifesting with dysphagia due to stenosis, or esophageal ulceration, with perforation in the extreme cases.

**6.9.3** Central Airway/Bronchial Injury

This bronchial injury with subsequent focal collapse of lung may impair overall pulmonary status. It also makes further assessment of tumor response more difficult as the collapsed lung approximates the treated tumor. Because atelectatic lung and tumor have similar imaging characteristics, radiology reports will often describe the overall process as progressive disease while the actual tumor may be stable or shrinking. Investigators are referred to the strict criteria for progressive disease in Section 11 of this protocol to avoid such mis-characterization.

**(7/27/10)** The consequences of bronchial toxicity, e.g., cough, dyspnea, hypoxia, impairment of pulmonary function test parameters, pleural effusion or pleuritic pain (associated with collapse), should all be graded according to the Common Terminology Criteria for Adverse Events (CTCAE), v. 4; MedDRA, v. 12.0.

**6.9.4** Lung Injury

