Patients enrolled to this study are allowed to have some degree of impaired pulmonary function as measured by pulmonary function tests (PFTs), including Forced Expiratory Volume in 1 second (FEV1), Forced Vital Capacity (FVC), and Diffusing Capacity for Carbon Monoxide (DLCO). The Common Toxicity Criteria (CTCAE), v. 4 includes specified criteria for grading adverse events related to these PFT parameters under the system organ class of Investigations. The grading criteria for these PFT changes use the “percent predicted” values from 0-100% which are recorded on the patient’s PFT report. A percent predicted of 90% conveys that the patient is able to perform the PFT test to a result that is 90% of what would be expected for the normal general population of the same height, age, and sex. The CTCAE version 4 specified grading criteria for PFTs assumes that all patients have normal baseline pulmonary function. This assumption is not appropriate for this protocol enrolling patients with abnormal baseline function.

[figure not shown]
As a remedy to monitor treatment effects on PFTs, we will define a protocol specific toxicity classification for PFTs that adjusts for baseline abnormalities. Changes that occur after therapy will be referenced to the baseline for a given patient, which will be abnormal for most patients. We have defined a proportional decline from the baseline. Grade 1 toxicity will be a

decline from baseline to a level 0.90 times the baseline, grade 2 will be a decline to a level 0.75 of baseline, grade 3 will be a decline to a level 0.5 of baseline, grade 4 will be a decline to a level 0.25 of baseline, and grade 5 will be death. This scheme is depicted in the table below and graphically represented in the figure below.

As an example, a patient who enters the study with a percent predicted DLCO of 55% who experiences a post treatment decline to a percent predicted DLCO of 40% would have a grade 3 event in the original CTCAE version 4 criteria; however, under this modified PFT toxicity classification for patients with abnormal baseline, his decline would constitute a decrease to 0.72 of the baseline value which is between 0.75 and 0.5 or a grade 2 event.

The SBRT Pulmonary Toxicity Scale					
Adverse Event	Grade				
	1	2	3	4	5
FEV-1 Decline	0.90-0.75 times the patient's baseline value	<0.75-0.50 times the patient's baseline value	<0.50-0.25 times the patient's baseline value	<0.25 times the patient's baseline value	Death

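### Secondary toxicity endpoints and Section 6.9.3 grade lung-function decline by CTCAE v4, although Section 6.9.5 replaces that grading with a baseline-referenced scale

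*Protocol*

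**What the plan says.** **The replacement scale (Section 6.9.5).** The protocol explains that the CTCAE v4 PFT criteria work from percent-predicted values and presuppose normal lung function at baseline. It then says: "This assumption is not appropriate for this protocol enrolling patients with abnormal baseline function". As the remedy, "we will define a protocol specific toxicity classification for PFTs that adjusts for baseline abnormalities". The result is the SBRT Pulmonary Toxicity Scale, which grades FEV1, FVC and DLCO by the ratio of the post-treatment value to the patient's own baseline.

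**Where that scale is invoked.** The DLT definition in Section 13.1.1 opens with CTCAE v4 and then names the SBRT scale, grades 3 to 5, for FEV1 and FVC decline. The special-reporting list in Section 6.10.2 does the same. DLCO is on the scale but in neither list.

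**Where CTCAE v4 is used instead.**
- Section 6.9.3, on the consequences of bronchial toxicity, includes "impairment of pulmonary function test parameters, pleural effusion or pleuritic pain (associated with collapse), should all be graded according to the Common Terminology Criteria", version 4.
- Section 13.5.3.1, the first-year non-DLT endpoint: "This endpoint is defined as any grade 3 or worse toxicity (per CTCAE, v. 4) other than a DLT".
- Section 13.5.3.2, the late endpoint: "This endpoint is defined as any grade 3 or worse toxicity (per CTCAE, v. 4) that is possibly, probably or definitely related to treatment".
- Objective 2.2.1 is likewise worded in terms of CTCAE v4 grade 3 or higher.

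None of these four places makes a PFT exception or refers to Section 6.9.5.

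**The concern.** A site holding one PFT report has two instructions that can give different grades. The patients in whom they diverge are the ones this trial enrols: Section 3.1.2.2 lists FEV1 below 40% predicted and severely reduced diffusion capacity among the standard reasons for medical inoperability.

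Two kinds of result are exposed:

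- **DLCO decline.** It is not in the DLT list. Short of a grade 5 event attributed to treatment, it can count only in the secondary toxicity endpoints, where the wording calls for CTCAE v4.
- **FEV1 or FVC decline.** A fall that is grade 2 on the protocol scale is not a DLT. If CTCAE v4 grades the same fall as 3, it meets the definition of a grade 3 toxicity other than a DLT.

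At stake is what the first-year non-DLT grade 3 or worse rate means. The DLT rate beside it grades PFT decline on one scale, while this rate would grade PFT decline on the scale whose premise the protocol rejects, or on a mixture if sites follow different sections.

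**Working it through.** **Inputs**
- Protocol scale, table in Section 6.9.5: grade 1 = 0.90 to 0.75 of baseline; grade 2 = below 0.75 to 0.50; grade 3 = below 0.50 to 0.25; grade 4 = below 0.25.
- Worked example, Section 6.9.5: DLCO 55% predicted at baseline, 40% after treatment. The protocol says this patient "would have a grade 3 event in the original CTCAE version 4 criteria" but has a ratio of 0.72 and grade 2 on its own scale.
- PFT schedule, Appendix II: 6 and 12 months after the start of SBRT.

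**Step 1: reproduce the protocol's figure.** Ratio = post-treatment value / baseline value = 40/55 = 0.727. The protocol prints 0.72 (truncated; it rounds to 0.73). The ratio lies between 0.50 and 0.75, so grade 2. The example is confirmed.

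**Step 2: apply each rule to that patient, assuming the event is judged treatment-related.**
- Sections 2.2.1 and 13.5.3.1 as written (CTCAE v4): grade 3, counted.
- Section 6.9.5 scale: grade 2, not counted.

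**Step 3: see how wide the disagreement is.** The CTCAE v4 cut-points are not in the protocol, so I use only its statement that 40% predicted DLCO is grade 3. I assume that this grade depends on the percent-predicted value reached, which is how Section 6.9.5 describes the criteria. With the post-treatment value held at 40%:

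| Baseline DLCO (% predicted) | Ratio | Protocol-scale grade |
|---|---|---|
| 45 | 40/45 = 0.89 | 1 |
| 50 | 40/50 = 0.80 | 1 |
| 55 | 40/55 = 0.73 | 2 |
| 60 | 40/60 = 0.67 | 2 |
| 70 | 40/70 = 0.57 | 2 |
| 80 | 40/80 = 0.50 | 2 |
| 90 | 40/90 = 0.44 | 3 |

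Under that assumption the two scales agree on grade 3 only for baselines above 80%. At 45% or 50% they differ by two grades.

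**Step 4: the band of disagreement for the example patient.** From a baseline of 55%, the protocol scale reaches grade 3 only below 0.50 × 55 = 27.5% predicted. If a lower percent predicted is never graded less severely under CTCAE v4, every result from 27.5% to 40% is grade 2 on one scale and at least grade 3 on the other.

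**Step 5: locate the exposure in time.** Both scheduled post-treatment PFTs fall within the first year or at its boundary. Section 13.5.3.1 covers the first year and Section 13.5.3.2 the period after it, so the first-year endpoint carries nearly all the exposure. The late endpoint is touched only by unscheduled PFTs or a 12-month test done slightly late.

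**The case against.** The best defence is that Section 6.9.5 governs throughout and Section 13.5.3 merely lacks a cross-reference. Section 6.9.5 is not worded as limited to DLTs. Section 13.1.1 itself opens with CTCAE v4 and then uses the SBRT scale for PFTs, so a general reference to CTCAE can coexist with the specific rule. The scale also has a DLCO row, which would have almost no use if only DLTs were graded on it. An analysis plan not shown here could state how PFT grades are derived for the tables.

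This is a fair account of what the authors probably intended, and it supports the direction of the fix. It does not remove the conflict. Section 6.9.3 names PFT impairment and sends it to CTCAE v4. It carries the same date mark (7/27/10) as Section 6.9.5, so neither can be read as the later correction. Section 13.1.1 states its exception explicitly; Section 13.5.3 does not. An analysis plan could regrade at the analysis stage, but it would not change what sites are told to record.

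Several stronger readings are tempting but not supported:

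- **That the MTD is affected.** The DLT definition has its own PFT item, which names the protocol scale.
- **That RTOG 0236 shows the size.** Section 1.2 reports some PFT-related grade 3 events there, but gives no baseline or post-treatment values from which to regrade them. That trial excluded tumors in the zone of the proximal bronchial tree and, per Section 13.2, used CTCAE v3.0.
- **That low baseline function alone would count as toxicity.** Both endpoints require an event at least possibly related to treatment.
- **That dose levels could not be compared.** One scale applied at analysis would apply to every level.
- **That the biomarker endpoints share the contradiction.** Sections 2.3.1 and 13.1.4.1 refer to grade 2 or higher pulmonary events without naming CTCAE.

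**Conclusion.** The concern holds as a contradiction between sections. Sections 6.9.3 and 6.9.5 give incompatible grading rules for the same PFT result. Objective 2.2.1 and endpoints 13.5.3.1 and 13.5.3.2, as worded, follow the rule whose underlying assumption Section 6.9.5 rejects. What is rejected is the normal-baseline assumption in the PFT criteria, not CTCAE v4 as a whole.

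For an individual patient the size is shown by the protocol's own example: one grade, across the grade 3 threshold. At lower baselines it is two grades, under the assumption in Step 3. For the trial, the number of patients reclassified cannot be estimated, because it depends on baseline and follow-up PFT values that the document does not give. The numerical demonstration is for DLCO only; for FEV1 and FVC the same route exists in the wording, but the CTCAE cut-points needed to illustrate it are not in the protocol.

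The consequence is confined mainly to the first-year non-DLT grade 3 or worse rate. Dose assignment, the MTD and the phase II tumor-control endpoint are untouched. This should be corrected, but it is not a design flaw.

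**What to change.** In Sections 2.2.1, 13.5.3.1 and 13.5.3.2, replace the bare CTCAE reference with: *per CTCAE v. 4, except FEV1, FVC and DLCO decline, which are graded by the SBRT Pulmonary Toxicity Scale (Section 6.9.5)*. In Section 6.9.3, take PFT impairment out of the CTCAE sentence and point it to Section 6.9.5, so that sites have one instruction. If CTCAE-graded PFT results are wanted for comparison with other trials, report them in a separate, descriptive table.

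The cost is wording in four places. PFTs are already scheduled at baseline, 6 and 12 months, so results graded on the wrong scale can be regraded by program, provided that the values themselves are recorded and not only the grades. No added visits or tests and no change to treatment rules are needed.
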